Successful treatment of ARDS associated with COVID-19 will likely require co administration of drugs with complementary mechanisms of action targeting different components of the disease, such as antiviral compounds to control viral replication (e.g., remdesivir) combined with drugs with the potential to address the pathophysiology of ARDS, in addition to respiratory support measures. Therefore, treatment with investigational COVID-19 therapies available under EUA by the FDA may be allowed, pending review and approval by the Medical Monitor and Sponsor Study Director. Key considerations for allowing co-administration of PLN-74809 with investigational COVID-19 therapies under EUA will include the potential for drug interactions and adverse drug reactions. Treatment with off-label use of any other drugs, devices, or interventions that might be used to manage COVID-19 may also be allowed, pending review and approval by the Medical Monitor and Sponsor Study Director.

Participants who discontinue study drug (regardless of reason) prior to completion of up to 14 days of treatment will be encouraged to remain in the study to complete all remaining assessments until hospital discharge or Day 28, whichever is sooner. If this is not feasible, they will be asked to perform an Early Termination (ET) visit for follow-up evaluations.

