**Figure 1. Study Schematic**

Non-ventilated participants will take study drug orally. Ventilated participants will receive study drug through a nasogastric (NG) or nasoenteric (NE) tube. Once participants are discharged from the hospital, they will no longer be administered study drug.

Successful treatment of ARDS associated with COVID-19 will likely require co-administration of drugs with complementary mechanisms of action targeting different components of the disease, such as antiviral compounds to control viral replication (e.g., remdesivir) combined with drugs with the potential to address the pathophysiology of ARDS, in addition to respiratory support measures. Therefore, treatment with investigational COVID-19 therapies available under EUA by the FDA may be allowed, pending review and approval by the Medical Monitor and Sponsor Study Director. Key considerations for allowing co-administration of PLN-74809 with investigational COVID-19 therapies under EUA will include the potential for drug interactions and adverse drug reactions. Treatment with off-label use of any other drugs, devices, or interventions that might be used to manage COVID-19 may also be allowed, pending review and approval by the Medical Monitor and Sponsor Study Director.

Participants who discontinue study drug for regardless of reason prior to completion of up to 14 days of treatment will be encouraged to remain in the study to complete all remaining assessments until hospital discharge or Day 28, whichever is sooner. If this is not feasible, they will be asked to perform an Early Termination (ET) visit for follow-up evaluations.

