#### **7.12 *Adverse Event Assessments***

All AEs observed by the Investigator, volunteered by the participant, or elicited through open-ended questioning of the participant from the time the informed consent form (ICF) is signed at the screening visit through Day 28 are to be recorded. Any SAEs must be reported to the Sponsor within 24 hours of Investigator first awareness of the event. All AEs, including SAEs, must be followed to resolution or until the Investigator determines that there is not an anticipated resolution. Definitions of AEs and the procedures for documenting and reporting AEs and SAEs are described in [Section 8](#).

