## 8 ADVERSE EVENTS

### 8.1 Timing

In this study, AEs will be collected from the time the participant signs the ICF until the Day 28 study visit.

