## 11 EARLY DISCONTINUATION OF STUDY OR INDIVIDUAL PARTICIPANTS

The Investigator may withdraw a participant from the study or discontinue study drug for any of the following reasons:

- Noncompliance with protocol procedures, including those relating to administration of study drug
- Occurrence of an SAE or intolerable AE
- Occurrence of a clinically significant change in a laboratory parameter
- [REDACTED]
- [REDACTED]
- Termination of the study by the Sponsor or Investigator
- The participant requests to be discontinued from the study

Participants who discontinue study drug (regardless of reason) will be asked to remain in the study to complete all remaining assessments until hospital discharge or Day 28, whichever is sooner, unless they withdraw consent or are lost to follow-up. If this is not feasible, the participant will be assessed for an early termination visit. All assessments that are required at the last study visit, as shown in [Appendix 1](#), should be completed for any participant who is withdrawn from the study or prematurely discontinues study drug and does not agree to complete all remaining assessments.

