### 12.5 Primary Endpoint

The primary endpoint is the nature and proportion of TEAEs between PLN-74809 and placebo groups (descriptive).

Safety data from all participants who received at least one dose of study drug will be incorporated into the final safety analysis. Further details of the safety analyses will be provided in the SAP. AEs will be collected from the time the participant signs the ICF until Day 28. TEAEs are defined as AEs that emerged or worsened in severity after the first administration of study drug.

AEs will be coded using the Medical Dictionary for Regulatory Activities (MedDRA®). All AEs will be graded for severity per the CTCAE grading scale and listed by participant and summarized by last treatment taken at onset of AE. All AEs will be listed by participant and summarized by last treatment taken at onset of AE.

The incidence of AEs, the incidence of TEAEs, the incidence of treatment-related AEs, and the severity of AEs will be summarized by system organ class, preferred term, and maximum severity. In cases where a participant reports multiple occurrences of the same event (preferred term), the greatest severity will be included in the summary. The number and percentage of participants with SAEs and treatment-related SAEs and participants who withdraw prematurely due to an AE will be tabulated by study treatment and dose.

Clinical laboratory test parameters will be graded using the CTCAE grading scale for individual participants and values outside the reference ranges will be flagged. The incidence of treatment-emergent laboratory abnormalities will be summarized by severity and treatment group. For each parameter, summary statistics will be calculated for each measure and summarized by treatment and dose.

[REDACTED]

Vital sign measurements, other laboratory tests, concomitant medications, medical history and changes in physical examinations at each time point will be listed by participant.

[REDACTED]

Concomitant medications will be coded using the most current WHO drug dictionary available.

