7.2 Adverse Events

An AE is any event, side effect, or other untoward medical occurrence that occurs in conjunction with the use of a study drug in humans, whether or not considered to have a causal relationship to this treatment. An AE can, therefore, be any unfavorable and unintended sign (that could include a clinically significant abnormal laboratory finding), symptom, or disease temporally associated with the use of a study drug, whether or not considered related to the study drug.

AEs will be coded using the MedDRA (version 23.0) and collected from the time the participant signs the informed consent form (ICF) until Day 28.

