7.2.5 Adverse Event Summaries

All AEs (serious and non-serious) occurring after study drug administration and by Day 28 of the study, regardless of relationship to study drug, will be included and classified by SOC and PT using MedDRA.

For TEAEs, the following will be summarized and presented for the Safety Set.

- i. An overall summary of TEAEs, which includes:
 - a. the number and percentage of participants experiencing a TEAE
 - b. the number and percentage of participants experiencing a TEAE by strongest relationship to investigational product
 - c. the number and percentage of participants experiencing a TEAE by strongest relationship to trial procedure
 - d. the number and percentage of participants experiencing a TEAE by greatest severity
 - e. the number and percentage of participants experiencing a TEAE with NCI CTCAE version 5.0 Grade 3 or higher
 - f. the number and percentage of participants experiencing a treatment emergent serious adverse event (TESAE)
 - g. the number and percentage of participants experiencing a TESAE by strongest relationship to investigational product
 - h. the number and percentage of participants experiencing a TESAE by strongest relationship to trial procedure

- i. the number and percentage of participants experiencing a TEAE leading to death
- j. the number and percentage of participants experiencing a TEAE which leads to a premature withdrawal
- ii. the number and percentage of participants experiencing a TEAE by SOC and PT
- iii. the number and percentage of participants experiencing a TEAE by SOC, PT and the strongest relationship to investigational product
- iv. the number and percentage of participants experiencing a TEAE by SOC, PT and the strongest relationship to trial procedure
- v. the number and percentage of participants experiencing a TESAE by SOC, PT and the strongest relationship to trial procedure

In the overall summary of TEAEs table (i), besides tabulating the number and percentage of participants, the total number of TEAE episodes will also be provided. If a participant has repeated episodes of a particular TEAE, all episodes will be counted in the summary table.

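### Does the rule for participants who stop study drug end their follow-up at discharge, before the Day 28 adverse-event window closes and the Day 90 contact?

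*Protocol*

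**What the plan says.** Four places give the rule for a participant who stops study drug early. The Protocol synopsis says such participants "will be encouraged to remain in the study to complete all remaining assessments until hospital discharge or Day 28, whichever is sooner". Protocol 3.1, in the text after the study schematic, repeats that they are encouraged to "complete all remaining assessments until hospital discharge or Day 28, whichever is sooner". Protocol Section 11 asks them to "complete all remaining assessments until hospital discharge or Day 28, whichever is sooner, unless they withdraw consent or are lost to follow-up", and SAP 3.2.4 carries the Section 11 clause unchanged.

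The adverse-event (AE) window is set separately, with no reference to discharge:

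- Protocol 7.12: AEs "from the time the informed consent form (ICF) is signed at the screening visit through Day 28 are to be recorded". The same section requires AEs to be followed until they resolve or the Investigator expects no resolution.
- Protocol 8.1: "AEs will be collected from the time the participant signs the ICF until the Day 28 study visit".
- Protocol 12.5, on the primary endpoint: "AEs will be collected from the time the participant signs the ICF until Day 28".
- SAP 7.2: AEs are "collected from the time the participant signs the informed consent form (ICF) until Day 28".
- SAP 7.2.5 summarises AEs "occurring after study drug administration and by Day 28 of the study, regardless of relationship to study drug".

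Protocol Appendix 1 and SAP Appendix A hold the schedule of events. Footnote c says that once a participant is off drug and discharged, the other assessments can be skipped, but the Day 28 and Day 90 phone contacts or record reviews stay. Footnote b adds medical records as a source for those contacts. SAP footnote e has ventilator and intensive-care use taken from records after discharge. Protocol 3.1 and SAP 3.1 describe 90 days of follow-up. SAP 5.1 tabulates completion status by arm without saying which contact marks completion.

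**The concern.** The clause ends at the earlier of two dates, and in this population discharge may well come before Day 28. A site that read Section 11 alone could close the record of an early stopper at discharge. Treatment-emergent AEs (TEAEs) between discharge and Day 28 would then go unrecorded, and Day 90 vital status would be missing.

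TEAEs are the primary endpoint. SAP 7.2.5 divides by the whole Safety Set and SAP 4.4 imputes no safety data, so an unrecorded event counts as no event. Stopping is also not a random matter: Section 11 lists serious or intolerable AEs and laboratory changes among the reasons. In arms this small, one missed participant visibly moves a proportion. The undefined completion status in SAP 5.1 adds to the doubt about which follow-up was expected.

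**Working it through.** **The plan's own duration.** Protocol 3.3 gives participation of up to about 107 days. Its parts are screening of up to 3 days, treatment of up to 14 days and follow-up of 90 days: 3 + 14 + 90 = 107, which reproduces the figure. If the clause ended participation, an early stopper would have at most 3 + 28 = 31 days. Protocol 3.3 makes no such distinction between early stoppers and others.

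**The literal reading.** Let D be the discharge day. The clause ends at min(D, 28). AE days lost are 28 − min(D, 28), and days short of the Day 90 contact are 90 − min(D, 28). The documents give no discharge days, so the values of D are assumptions.

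| Assumed discharge day | Clause ends | AE days lost before Day 28 | Days short of Day 90 |
|---|---|---|---|
| 7 | 7 | 21 | 83 |
| 10 | 10 | 18 | 80 |
| 14 | 14 | 14 | 76 |
| 21 | 21 | 7 | 69 |
| 28 or later | 28 | 0 | 62 |

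**Do the texts force that reading?** There are two groups of early stoppers.

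1. *Discharged before Day 28.* Footnote c addresses exactly this participant and names the Day 28 and Day 90 contacts as the ones that may not be dropped. Section 11 itself refers the site to Appendix 1, and Protocol Section 7 makes Appendix 1 the schedule.
2. *Still in hospital at Day 28.* Here the clause runs to Day 28, so the AE window is complete and the primary endpoint is untouched. Footnote c is a permission to omit; a participant outside its terms keeps the ordinary schedule, which marks vital status at the phone contacts.

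The clause asks people to stay in the study and complete assessments up to a point. It does not say that later contact or AE collection stops. If it limits scheduled in-hospital assessments, every passage can be obeyed at once and the AE days lost are 0 for anyone who neither withdraws consent nor is lost to follow-up. The provisions for medical-record data fit that reading.

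SAP 3.2.4 sets no competing analysis rule. SAP Section 1 says that its Sections 2 and 3 describe the study as the Protocol has it. The analysis window is in SAP 7.2.5 and runs to Day 28.

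**Weight of one participant.** In a cohort as planned (9 on PLN-74809, 3 on placebo), one wrongly event-free participant moves the arm's TEAE proportion by 1/9 = 11.1 percentage points or 1/3 = 33.3 percentage points. These are the steps for any one person in arms of that size, whatever the cause. For the clause to produce one, a participant must stop drug early, leave hospital before Day 28, have no TEAE before discharge, have one afterwards, and have it missed by a site that disregards footnote c and the AE sections.

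**The case for a change.** The best case for a change has three parts. First, footnote c preserves contacts but does not name AE collection, and it is conditional on discharge. Second, a missed event is counted as no event in the primary summary. Third, SAP 5.1 leaves two programmers free to classify a discharged early stopper differently, and this can still be put right at the cost of one definition and two counts per arm (AE follow-up to Day 28 and Day 90 vital status).

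On the first part, AE collection does not depend on footnote c: Protocol 7.12, 8.1 and 12.5 require it to Day 28 for everyone, and the retained Day 28 contact gives the occasion. The AE row of the schedule has no legible marks in the public text, and Protocol Sections 9 and 10 and some footnotes are blacked out, so these cannot settle the matter either way.

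The second part is right about the mechanism but needs a site to set aside several explicit duties, and nothing in the documents shows that this happened.

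The third part stands as missing detail. SAP 5.1 already tabulates completion status and reasons for early termination by arm, with a listing; SAP 5.2 lists protocol deviations, and the AE listing carries onset and resolution days. Whoever programs the disposition table must settle what completion means and can state it in a table note. The two extra counts would help a reader, but they are a reporting preference.

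**Conclusion.** The four passages lack a cross-reference to the AE window and to footnote c, and their wording does not match either. That is a clerical inconsistency. Read as a whole, the plan still requires AE collection to Day 28 and contacts at Days 28 and 90 for early stoppers, so the TEAE summary rests on a sound window.

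Rewording would bring no practical gain. SAP Section 4 records that the sponsor has terminated the study, so new text cannot recover any contact, and the analyses are descriptive with no hypothesis tested. The open point on completion status is a gap that analysts fill sensibly.

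The actual loss, if any, cannot be derived: the documents give no rates of discontinuation or discharge and no numbers treated. The 21-day figure assumes discharge on Day 7 and a site that reads the clause alone. The 11.1- and 33.3-point steps assume the planned 9 and 3 participants and would be larger with fewer treated. The conclusion rests on the visible text and on sites having followed the schedule footnotes and the AE sections together.

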## 12 PLANNED STATISTICAL METHODS

### 12.1 General Considerations

No statistical hypotheses will be tested. Data will be summarized with descriptive statistics. Graphic presentations may also be prepared. All data will be listed by treatment group and participant.

A statistical analysis plan (SAP), which will provide a detailed analysis plan, will be prepared and approved before database lock. Where different, the analyses described in the statistical analysis plan will supersede those described in the protocol.

### 12.2 Determination of Sample Size

A large rectangular area of the page is completely blacked out, indicating that the original content has been redacted.

### 12.3 Analysis Populations

Two analysis populations will be defined:

- Safety Population: all randomized participants who receive at least 1 dose of study drug.
- PK Concentration Population: all randomized participants who receive at least 1 dose of study drug and have any measurable PLN-74809 concentration data.

### 12.4 Demographics and Baseline Characteristics

Demographic data will be summarized descriptively (n, mean, standard deviation, median, minimum, and maximum) by treatment group. Medical history and prior and concomitant medication data will be listed by treatment group and participant.

### 12.5 Primary Endpoint

The primary endpoint is the nature and proportion of TEAEs between PLN-74809 and placebo groups (descriptive).

Safety data from all participants who received at least one dose of study drug will be incorporated into the final safety analysis. Further details of the safety analyses will be provided in the SAP. AEs will be collected from the time the participant signs the ICF until Day 28. TEAEs are defined as AEs that emerged or worsened in severity after the first administration of study drug.

AEs will be coded using the Medical Dictionary for Regulatory Activities (MedDRA®). All AEs will be graded for severity per the CTCAE grading scale and listed by participant and summarized by last treatment taken at onset of AE. All AEs will be listed by participant and summarized by last treatment taken at onset of AE.

The incidence of AEs, the incidence of TEAEs, the incidence of treatment-related AEs, and the severity of AEs will be summarized by system organ class, preferred term, and maximum severity. In cases where a participant reports multiple occurrences of the same event (preferred term), the greatest severity will be included in the summary. The number and percentage of participants with SAEs and treatment-related SAEs and participants who withdraw prematurely due to an AE will be tabulated by study treatment and dose.

Clinical laboratory test parameters will be graded using the CTCAE grading scale for individual participants and values outside the reference ranges will be flagged. The incidence of treatment-emergent laboratory abnormalities will be summarized by severity and treatment group. For each parameter, summary statistics will be calculated for each measure and summarized by treatment and dose.

[REDACTED]

Vital sign measurements, other laboratory tests, concomitant medications, medical history and changes in physical examinations at each time point will be listed by participant.

[REDACTED]

Concomitant medications will be coded using the most current WHO drug dictionary available.

## 12.6 Secondary Endpoints

### 12.6.1 Secondary Pharmacokinetic Endpoints

Plasma PLN-74809 concentrations (total and unbound concentrations) at each sampling timepoint will be presented in listings and descriptive summary statistics by dose and visit. The data will also be presented graphically.

Further details of the analyses will be provided in the SAP to be prepared and agreed prior to final 'database lock' at the end of the study. The PK analysis plan and report may be prepared separately from the SAP as appropriate.

## 12.7 Exploratory Endpoints

A horizontal bar chart with 10 bars of varying lengths. The bars are black on a white background. The lengths of the bars decrease from left to right. The first bar is the longest, followed by a short bar, then a long bar, then a medium bar, then a very long bar, then a short bar, then a long bar, then a medium bar, then a very long bar, and finally a short bar.

## 12.8 Interim Analysis

No interim analyses are planned.

### **13 QUALITY CONTROL AND ASSURANCE**

During the study, the Sponsor and/or representatives of the Sponsor may visit the site to conduct an audit of the study. The purpose of this visit will be to determine the Investigator's adherence to the protocol, applicable regulations, and the Sponsor's procedures, in addition to assessing the accuracy of the study data. Prior to initiating this audit, the Investigator will be contacted by the Sponsor to arrange a convenient time for this visit. The Investigator and staff are expected to cooperate with the auditors and to allow access to all participant records supporting the eCRFs and other study-related documents.

At some point during the development program for the study drug, a regulatory authority may visit the Investigator to conduct an inspection of the study and the site. The Investigator and staff are expected to cooperate with the inspectors and to allow access to all source documents supporting the eCRFs and other study related documents. The Investigator must immediately notify the Sponsor when contacted by any regulatory authority for purposes of conducting an inspection.

## **14 ADMINISTRATIVE CONSIDERATIONS**

### **14.1 Institutional Review Board, Independent Ethics Committee Approval, or Research Ethics Board Approval**

The Investigator must inform and obtain approval from the IRB/IEC/REB for the conduct of the study at named sites, for the protocol, for the participant ICF and any other written information that will be provided to the participants, and any advertisements that will be used. Written approval must be obtained prior to recruitment of participants into the study and shipment of investigational agent.

Proposed amendments to the protocol and aforementioned documents must be discussed among the Sponsor and contract research organization (CRO) personnel, submitted to the IRB/IEC/REB for approval, and then submitted to regulatory authorities for approval prior to implementation. Amendments may be implemented only after a copy of the local IRB/IEC/REB approval letter has been transmitted to the Sponsor. Amendments that are intended to eliminate an apparent immediate hazard to participants may be implemented prior to receiving Sponsor or IRB/IEC/REB approval. However, in this case, approval must be obtained as soon as possible after implementation.

The Investigator will be responsible for reporting protocol deviations to the IRB/IEC/REB as required by local requirements. The Investigator will be responsible for ensuring that an annual update is sent to the IRB/IEC/REB to facilitate continuing review of the trial (if needed) and that the IRB/IEC/REB is informed about the end of the study. Copies of the update, subsequent approvals, and final letter must be sent to the Sponsor.

